In view of the high efficacy of cemiplimab against advanced CSCC and the positive phase 3 results among other anti-PD-1 antibodies in the adjuvant setting for melanoma patients, it is appropriate to evaluate cemiplimab in the post-operative setting. Therefore, Part 2 of this protocol allows adjuvant cemiplimab in patients who have not experienced disease progression or unacceptable toxicity during Part 1 (the neoadjuvant portion) of the study. An investigator, according to his or her clinical judgment, may opt to administer adjuvant radiation therapy in this study instead of adjuvant cemiplimab in Part 2. Such patients will not receive cemiplimab after this therapy but should be followed for disease recurrence and survival during the study. The data from Part 2 could inform the development of a future randomized trial to define adjuvant therapy for patients

with CSCC. However, the primary objective of this study is to assess neoadjuvant cemiplimab, not adjuvant therapy.

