8.7.1. Prohibited Medications and Procedures

While participating in this study (not including survival follow-up), a patient may not receive any of the following medications from the time of informed consent to the end of the follow-up period, unless otherwise specified below:

- Standard or investigational agent (other than cemiplimab) for treatment of a tumor, with the exception of those listed in Section 8.7.2
- Live vaccines for at least 3 months after the last dose of study drug

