11.3. Subgroup Analyses

Subgroup analyses will be performed to determine the consistency of treatment effect across various demographics and baseline characteristics. Between-group treatment effect, along with its nominal 95% CI, for the primary endpoint will be estimated within each category for the following subgroups:

- Age (<65 years, ≥65 years)
- Gender (Male, Female)
- Race (White, Non-white)
- Anatomic region of resected tumor (HN, Non-HN)
- Tumor stage (II, III/IV)
- ECOG status (0, 1)

As regards the DFS endpoint, a descriptive comparison will be performed between subgroups of patients who receive adjuvant cemiplimab versus adjuvant radiation therapy versus observation after surgery.

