4.3. Pre-Treatment / Concomitant Medication

Medications/Procedures will be recorded from the day of informed consent until the end-of-study (EOS) visit. Medications will be coded using WHO Drug Dictionary (WHODD).

Prior cancer related medications/procedures: medications taken, or procedures performed prior to administration of the study drug.

Pre-treatment medications/procedures: non-study medications for which administration started and discontinued before a patient received the first dose of study drug.

Concomitant medications/procedures: any treatment administered from the time of informed consent until 90 days after the last study treatment or start of another systemic anticancer therapy, whichever comes first, will be considered concomitant treatment. This includes medications that were started before the study and are ongoing during the study, as well as any therapies started in the follow-up period to treat treatment related AEs.

Post treatment anti-cancer medications/procedures: anti-cancer medications and other anti-cancer therapies that started after discontinuation of the study drug.

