4.4.2. Secondary Efficacy Variables

The secondary efficacy variables include:

- Major pathologic response (mPR) rate per independent central pathology review: mPR is defined as failure to achieve pCR but $\leq 10\%$ viable cancer cells in the surgical pathology sample.
- pCR rate and mPR rate assessed by local pathology review: pCR and mPR will be assessed by local pathology review.
- Objective response rate (ORR) prior to surgery by investigator assessment: ORR is determined by the proportion of patients with CR or PR based on investigator-assessed evaluation using RECIST 1.1 (Eisenhauer, 2009), where there is no requirement for confirmation of CR or PR. The objective response will be measured from the first dose of neoadjuvant cemiplimab to surgery or any other new anti-cancer therapy.
- Event free survival (EFS) is defined as time from first dose of neoadjuvant cemiplimab to the first of any of the following events: progression of disease that precludes surgery, inability to undergo complete resection (R0 or R1), disease recurrence (local, regional, or distant) for patients who undergo complete resection (R0 or R1), or death due to any cause.
 - Patients who do not have an EFS event without initiation of a new anti-cancer therapy will be censored at the last evaluable tumor assessment.
 - Patients who do not have an EFS event but initiate a new anti-cancer therapy, will be censored at the last evaluable tumor assessment prior to or on the date of new anti-cancer therapy.
 - Patients who do not have any evaluable post-baseline tumor assessment and do not die will be censored on the date of first study treatment.
- Disease free survival (DFS) is defined for patients who are free of disease (R0 or R1 resection) at completion of surgery as time from date of surgery until first recurrence (local, regional, or distant) or death due to any cause.
 - Patients who do not have recurrence of tumor and alive without initiation of a new anti-cancer therapy will be censored at the last evaluable tumor assessment.

- Patients who do not have recurrence of tumor and alive, but initiate a new anti-cancer therapy, will be censored at the last evaluable tumor assessment prior to or on the date of new anti-cancer therapy.
- Patients who do not have any tumor assessment after surgery and do not die will be censored on the date of surgery.

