4.5. Safety Variables

Patient safety will be assessed through the collection of reported adverse events (AEs), clinical laboratory data, vital signs, ECG, and physical exam.

The observation period will be divided into three segments: pre-treatment, on-treatment and post-treatment.

- The pre-treatment period is defined as the time from signing the ICF to before the first dose of study drug.
- The treatment period is defined as the time from the day of first dose of neoadjuvant cemiplimab to the day of the last dose of neoadjuvant cemiplimab plus 90 days or to 1 day before patients receive their first dose of adjuvant cemiplimab or another anticancer systemic therapy, whichever is earlier.
- The post-treatment period is defined as the time starting one day after the end of on treatment period.

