5.6.2. Analysis of Secondary Efficacy Variables

The pCR rate per local pathology review, mPR rate per independent central pathology review, mPR rate per local pathology review, and ORR prior to surgery per investigator assessment will be summarized and corresponding two-sided 95% exact CIs will be calculated by Clopper-Pearson method (Clopper, 1934).

Percent residual viable tumor (%RVT) will be summarized descriptively.

Combined efficacy based on both ORR per RECIST 1.1 and pCR and mPR per pathology review may be explored.

The distribution of EFS, DFS, and OS will be estimated using the Kaplan-Meier method. The median EFS, median DFS, and median OS along with 95% CIs will be presented and Kaplan-Meier estimates with 2-sided 95% CIs at specific time points will be summarized. The Kaplan Meier curves will be presented.

As regards the DFS endpoint, a descriptive summary will be performed for each subgroup of patients who receive adjuvant cemiplimab, adjuvant radiation therapy, and observation after surgery.

Change in planned surgery will be summarized descriptively. The proportion of patients for whom the surgical management plan (at time of screening) differed from the actual surgery after neoadjuvant therapy will be summarized both by investigator assessment and independent surgical expert committee.

Change in planned post-surgical management will be summarized descriptively. The proportion of patients for whom radiation therapy (or chemoradiation) was planned during screening but not actually administered after neoadjuvant cemiplimab and surgery will be summarized.

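### SAP 4.4.2 censors EFS and DFS at new anti-cancer therapy only in patients who never have an event, so censoring depends on outcome and the estimates read slightly low

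*SAP*

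**What the plan says.** SAP 4.4.2 gives the only EFS and DFS censoring rules in either document. For DFS: "Patients who do not have recurrence of tumor and alive, but initiate a new anti-cancer therapy, will be censored" at the last evaluable assessment on or before the new therapy. For EFS: "Patients who do not have an EFS event but initiate a new anti-cancer therapy, will be censored at the last evaluable tumor assessment", with the same cut-off. The event definitions contain no cut-off at new therapy.

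Neither document defines new anti-cancer therapy. Two nearby SAP terms differ in scope, and neither is linked to the censoring rule:

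- SAP 4.3, post-treatment therapy: "anti-cancer medications and other anti-cancer therapies that started after discontinuation of the study drug". This is not limited to systemic treatment.
- SAP 4.5, end of the safety treatment period: "first dose of adjuvant cemiplimab or another anticancer systemic therapy, whichever is earlier". This is limited to systemic treatment.

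Adjuvant radiation, with or without concurrent systemic agents, is a named Part 2 option (Protocol 6.1.3 and 8.7.2). Of irradiated patients, Protocol 3.2.3 says: "Such patients will not receive cemiplimab after this therapy but should be followed for disease recurrence and survival during the study". Protocol 9.1.6 schedules their imaging. Protocol 11.3 plans that "a descriptive comparison will be performed between subgroups of patients who receive adjuvant cemiplimab versus adjuvant radiation therapy versus observation" after surgery, and SAP 5.6.2 keeps this as "a descriptive summary will be performed for each subgroup of patients who receive adjuvant cemiplimab, adjuvant radiation therapy, and observation after surgery". Protocol 8.7.1 prohibits other tumor treatment to the end of follow-up: "Standard or investigational agent (other than cemiplimab) for treatment of a tumor, with the exception of those listed in Section 8.7.2".

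**The concern.** A time-to-event analysis can ignore new therapy and count everything, or it can stop the clock for everyone at new therapy. Each is coherent. The SAP wording, taken as written, mixes the two: whether a patient's clock stops depends on whether an event comes later. Follow-up is removed only from patients who did well, so the curves are pulled down by the rule and not by the disease or the treatment.

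The undefined term matters because it decides how many patients the rule touches. If it covers only non-protocol therapy, few are touched. If it also covered adjuvant radiation, a whole Part 2 group would be.

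**Working it through.** **1. The rule applied to two patients.** Both have complete resection and start the same new therapy at month 12, on the day of a clear scan. Patient A recurs at month 20. No censoring bullet applies, so A is an event at month 20. Patient B is event-free to month 48 and is censored at month 12.

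**2. Direction.** Kaplan-Meier multiplies factors 1 − d/n. The literal rule keeps every d and removes patients like B from n. Each factor after the cut is therefore lower or unchanged, so the estimate cannot exceed the one from full follow-up.

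**3. Inputs.** The plan states no EFS or DFS rate, so it has no figure to reproduce. Assumed: 70 patients with complete resection; exponential DFS with true 2-year DFS of 70, 80 or 90%; 48 months of follow-up; k = 1, 2 or 4 of the 70 on non-protocol therapy, affected if event-free at month 12; start of therapy unrelated to risk.

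**4. Non-protocol therapy.** A fraction c = (k/70) × S(48) of the cohort never has an event and is cut at month 12. At t > 12 the fraction at risk is S(t) − c, with the same events, so

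KM(t) = S(12) × [S(t) − c] / [S(12) − c].

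Example, true 70%, k = 4:
- S(12) = √0.70 = 0.8367; S(48) = 0.70² = 0.49; c = (4/70) × 0.49 = 0.0280.
- KM(24) = 0.8367 × 0.6720/0.8087 = 0.6953, which is 0.47 points low.
- S(36) = 0.70^1.5 = 0.5857; KM(36) = 0.8367 × 0.5577/0.8087 = 0.5770, which is 0.87 points low.

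Points low at 2 years:

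| True 2-year DFS | k = 1 | k = 2 | k = 4 |
|---|---|---|---|
| 70% | 0.12 | 0.23 | 0.47 |
| 80% | 0.10 | 0.20 | 0.40 |
| 90% | 0.06 | 0.12 | 0.25 |

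A simulation of the same model (40,000 replicates) agrees within 0.01 point. With recurrences dated to the scheduled scans and therapy starting at month 6, 12 or 18, the largest shift is 0.6 points at 2 years and 1.0 at 3 years. For EFS, adding six assumed events at day 85, the 2-year shift is 0.06 to 0.54 points. As a stress test, 5 to 20% of patients starting other therapy at a random time in months 1 to 36 lowers 3-year DFS by about 0.2 to 2 points.

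**5. If radiation were counted.** Let r of 70 be irradiated (r = 10, 15 or 25, assumed), starting before any post-surgery scan, so event-free irradiated patients are cut at surgery. Then c = (r/70) × S(48) and KM(24) = [S(24) − c]/(1 − c).
- r = 25, true 70%: c = 0.175; 0.525/0.825 = 0.636, 6.4 points low.
- r = 10, true 90%: c = 0.1157; 0.7843/0.8843 = 0.887, 1.3 points low.
- Radiation subgroup: [S(24) − S(48)]/[1 − S(48)] = 0.21/0.51 = 0.41, 0.16/0.36 = 0.44 and 0.09/0.19 = 0.47 for true 70, 80 and 90%.

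If radiation starts after the first required scan (30 + 21 + 105 = 156 days after surgery), simulation gives 1.0 to 5.2 points overall and 45 to 54% in the subgroup.

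**6. A symmetric rule.** If every starter is censored, events and numbers at risk fall in proportion and KM(t) returns S(t). In simulation it is within 0.02 point of full follow-up. That agreement depends on therapy start being unrelated to risk.

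**The case against.** The strongest reply is that the intent is plain and the effect negligible. With 70 patients, the 95% half-width for 2-year DFS is 1.96 × √[p(1 − p)/70] = 10.7, 9.4 and 7.0 points at 70, 80 and 90%. A shift of 0.47 against 10.7 is about 4% of that. EFS and DFS are descriptive, and the error understates efficacy. Protocol 8.7.1 closes most routes to non-protocol therapy before recurrence. Subsequent systemic therapy is collected in survival follow-up (Protocol 9.1.7), which begins after recurrence, incomplete resection or the end of scheduled imaging; by then the event has usually happened or little follow-up is left to lose. All of this stands, and it is why the point is minor. It does not alter the wording: no sentence limits events to those before new therapy, and the protocol has no censoring rule to fall back on.

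It is also fair that low is relative to a target. The shifts above are measured against full follow-up. Censoring every starter targets something else, and if higher-risk patients start new therapy it would itself read high. So neither coherent rule is the only right one.

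A reader might infer that irradiated patients will be censored, so that DFS is several points off or the radiation subgroup is emptied. The documents do not support this. They keep these patients in recurrence follow-up and plan a DFS summary for them, which censoring at radiation would defeat. Even on that reading, the literal rule would cut only event-free patients, so the subgroup would be skewed toward failure, not emptied. What remains is that SAP 4.4.2 never states the exclusion, and the SAP 4.3 term would take radiation in.

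**Conclusion.** The rule is wrong as written: censoring at new therapy depends on later outcome, and it lowers Kaplan-Meier EFS and DFS relative to full follow-up. On the likely meaning, non-protocol therapy only, DFS reads about 0.1 to 0.6 points low at 2 years and at most about 1 point low at 3 years. This rests on 1 to 4 of 70 patients starting such therapy, 2-year DFS of 70 to 90%, and therapy start unrelated to risk; none of these comes from the documents. Shifts of several points need adjuvant radiation to count, which is probably not intended. The missing definition alone is largely settled by context. The primary pCR analysis and N = 76 are untouched. Severity: minor.

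**What to change.** In SAP 4.4.2, for both EFS and DFS, choose one rule that does not depend on later outcome and run the other as a sensitivity analysis:

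- (a) Count all events and all follow-up regardless of new therapy; or
- (b) *Patients with no event on or before the start of new anti-cancer therapy are censored at the last evaluable tumor assessment on or before that start, whether or not an event follows.*

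Under (b), the words on or before matter. Protocol 9.2.2.6 can date a recurrence to the procedure that obtains the pathology sample. If that excision also treats the lesion, event and therapy share a date, and a rule reading only before would censor a real recurrence.

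Under (b), also note that the rule assumes starting new therapy is unrelated to risk. State that protocol-permitted adjuvant cemiplimab, adjuvant radiation or chemoradiation, and local treatment of second primary tumors are not new anti-cancer therapy. Without that exclusion, making the rule symmetric would strip the irradiated subgroup of nearly all follow-up and defeat its planned DFS summary.

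Cost: a few sentences in the SAP before database lock, and no new data.

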4. ENDPOINTS

For endpoints measuring pCR, mPR, and ORR (Part 1 of the study), patients will be assessed at the time of surgery (12 weeks). Event free survival (EFS) and OS will be assessed from the first dose of neoadjuvant cemiplimab until completion of follow-up. Disease free survival (DFS) will be assessed from surgery until completion of follow-up. Event free survival (EFS), DFS, and OS assessment will continue until all enrolled patients have completed follow-up, a total duration of approximately 4 years and 3 months.

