5.2. Efficacy Variables

5.2.1. Disease Response and Disease Recurrence

Disease response will be assessed by surgical pathology using pCR and mPR. Pathologic complete response (pCR) is defined as absence of viable cancer cells in the surgical pathology sample. Major pathologic response (mPR) is defined as $\leq 10\%$ viable cancer cells in the surgical pathology sample, in patients who have not achieved pCR. Procedures to assess pCR and mPR in the surgical pathology sample after neoadjuvant therapy are not described in this protocol but will be described in a separate charter.

Objective response rate (ORR) will be assessed by the investigator using RECIST 1.1 (Eisenhauer, 2009)(Appendix 4). Procedures for assessing ORR are outlined in Section 9.2.2.3. Confirmation of complete or partial response is not required.

Event free survival (EFS) is defined as time from first dose of neoadjuvant cemiplimab to any of the following events: progression of disease that precludes surgery, inability to undergo complete resection (R0 or R1), disease recurrence (local, regional, or distant) for patients who undergo complete resection (R0 or R1), or death due to any cause.

Disease free survival (DFS) is defined as time from surgery to first recurrence (local, regional, or distant) or death due to any cause, for patients who are free of disease (R0 or R1 resection) at completion of surgery. Patterns of failure in patients with local, regional, or distant disease recurrence will be assessed by descriptive analysis according to the procedures outlined in Section 9.2.2.5 and Section 9.2.2.6.

Overall survival (OS) will be measured as time from first dose of neoadjuvant cemiplimab to death due to any cause.

5.2.2. Changes in Planned Surgery and Post-Surgical Management (Per Investigator and Per Independent Review)

Electronic case report forms (eCRFs) will capture what the management plan would be for surgery and post-surgical management if the patient were not enrolled in a clinical trial, as well as the actual surgery that was performed and the actual post-surgical management.

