- Overall survival (OS) is measured from the start of treatment until death due to any cause. Patients who do not die will be censored at the last date that patient is documented to be alive.

For all the above time-to-event variables, the time to event (day) is the date of event/censor - the date of first study treatment + 1.

- Change in surgical plan in the screening period versus actual surgery after neoadjuvant cemiplimab both according to investigator review and independent surgical expert review is measured by descriptive analysis. For investigator review, the overall treatment plan formulated at a multidisciplinary tumor board, description of planned/actual surgery resection, description of planned/actual reconstruction (if applicable) and planned/actual length of inpatient hospital stay after surgery will be collected.
- Change in post-surgical management plan in the screening period versus actual post-surgical management both according to investigator review and independent surgical expert review is measured by descriptive analysis. For investigator review, radiotherapy method, radiation fractionation, duration of therapy, total dose, and adjuvant chemoradiation type (if applicable) will be collected.

For independent review, variables to assess changes in planned surgery and post-surgical management will be described in a separate charter.

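### The SAP's time-to-event formula starts the DFS clock at first dose, although DFS is defined from surgery, so about 12 event-free weeks are added

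*SAP*

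**What the plan says.** Three places set the start of DFS at surgery:

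- Protocol section 4: "Disease free survival (DFS) will be assessed from surgery until completion of follow-up".
- Protocol section 5.2.1: "Disease free survival (DFS) is defined as time from surgery to first recurrence (local, regional, or distant) or death due to any cause".
- SAP section 4.4.2: "time from date of surgery until first recurrence (local, regional, or distant) or death due to any cause", and only "for patients who are free of disease (R0 or R1 resection) at completion of surgery".

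The SAP's censoring rule for DFS fits that origin: "Patients who do not have any tumor assessment after surgery and do not die will be censored on the date of surgery".

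After the EFS, DFS and OS definitions, the same SAP section gives the computing rule. Its scope is "For all the above time-to-event variables" and its formula is that "the time to event (day) is the date of event/censor - the date of first study treatment + 1". DFS is not excepted. SAP section 1.2.4 lists two departures from the protocol (the definition of the full analysis set and the removal of subgroup efficacy analyses). A new origin for DFS is not among them.

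**The concern.** The definition and the computing rule for DFS cannot both be followed. The rule is the part a programmer would code from. If it is used, three things go wrong.

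- **Guaranteed event-free time.** A patient has to reach surgery and be resected R0 or R1 to enter the DFS analysis, so the time from first dose to surgery cannot contain a DFS event. Counting it can only move DFS upward.
- **Loss of a separate endpoint.** Once a patient has had an R0 or R1 resection, the EFS events still possible are recurrence and death, which are also the DFS events. With a common origin, DFS becomes essentially EFS restricted to resected patients.
- **Unequal shift between adjuvant groups.** SAP section 5.6.2 summarises DFS separately for adjuvant cemiplimab, adjuvant radiation and observation. Patients who stop neoadjuvant drug for progression or toxicity may go to surgery early (Protocol 6.1.2) and cannot receive adjuvant cemiplimab (Protocol 9.1.5.1). Those operated on early get a smaller excess, and among the three groups they can fall only in radiation or observation. The error can therefore flatter the cemiplimab group in a comparison that Protocol 3.2.3 says could inform a later randomised trial.

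**Working it through.** **Inputs**

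- Last planned neoadjuvant dose: day 64 (Protocol 6.1.2).
- Surgery 21 days after the last dose, window day 75 to day 100 (Protocol 9.1.1, footnote 9).
- Surgery assessed at 12 weeks (Protocol 4).
- End-of-Part-1 visit (EOT1) 30 days after surgery (Protocol Table 2), Part 2 week 0 three weeks after that visit, first Part 2 imaging at week 15 (Protocol 9.1 and Table 3).
- DFS rates: none in the documents, so these are assumed below.

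**Step 1: the plan's own interval.** 64 + 21 = day 85. From day 1, 85 − 1 = 84 days = 12.0 weeks, which agrees with the stated 12 weeks.

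**Step 2: excess per patient.** (event date − first dose + 1) − (event date − surgery + 1) = surgery date − first dose date = surgery day − 1. Months are 30.4375 days.

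| Surgery day | Excess (days) | Weeks | Months |
|---|---|---|---|
| 75 | 74 | 10.6 | 2.4 |
| 85 | 84 | 12.0 | 2.8 |
| 100 | 99 | 14.1 | 3.3 |
| 43 (assumed early surgery) | 42 | 6.0 | 1.4 |

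**Step 3: two example patients, surgery on day 85.**

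- Censored on the date of surgery: 85 − 85 + 1 = 1 day from surgery, against 85 − 1 + 1 = 85 days under the SAP formula. This patient has no postoperative tumour assessment at all.
- Recurrence at the first Part 2 imaging: 85 + 30 + 21 + 105 = day 241. DFS is 241 − 85 + 1 = 157 days from surgery, against 241 days under the SAP formula.

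**Step 4: effect on landmark rates.** If everyone has surgery on day 85, the reported rate at t months is the true rate at t − 2.76 months. A 12-month figure is therefore the rate at 12 − 2.76 = 9.24 months after surgery. Under a constant hazard, S(t) = S24^(t/24), where S24 is the assumed true 24-month DFS. The reported value is S24^((t − 2.76)/24).

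| Assumed 24-month DFS | 12 months: true | 12 months: reported | Excess (points) | 24 months: reported | Excess (points) |
|---|---|---|---|---|---|
| 70% | 83.7% | 87.2% | 3.5 | 72.9% | 2.9 |
| 80% | 89.4% | 91.8% | 2.3 | 82.1% | 2.1 |
| 90% | 94.9% | 96.0% | 1.2 | 91.1% | 1.1 |

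Excesses are taken before rounding. At 80%, moving surgery across the window changes the reported 12-month rate only from 91.5% (day 75) to 92.2% (day 100).

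**The case against.** The best reply is that this is a drafting slip. The SAP's own definition names surgery, its censoring rule treats surgery as time zero, and a careful programmer would follow the specific definition over a general sentence or raise a query. The bias arises only if the general sentence wins. That is fair, and it makes the effect conditional. It does not remove the contradiction, because the general sentence is the only formula given and it explicitly covers DFS. Resolving the conflict at the programming stage, in an open-label trial, is what a pre-specified plan should avoid.

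Three points on size also stand.

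- Twelve weeks is the planned value. Every DFS time is affected, but patients diverted to early surgery gain less, and they fall outside the 74 to 99 day range.
- The shift in the median may never be seen. Under a constant hazard the median is 24 × ln 2 / (−ln S24): about 47 months for 70%, 75 months for 80% and 158 months for 90%. Follow-up is about 4 years after surgery (Protocol 9.2.2.3), so landmark rates are where the error would show.
- DFS is a descriptive secondary endpoint. It carries no test, alpha or decision rule.

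These points limit the consequence. None of them makes the formula right for DFS.

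**Conclusion.** The concern holds. The SAP formula contradicts the definition of DFS in the same section and in the protocol, and nothing elsewhere corrects it. Followed literally, it lengthens each DFS time by that patient's interval from first dose to surgery. The date arithmetic rests only on the protocol schedule. The percentage-point figures also rest on an assumed constant hazard, assumed 24-month rates of 70% to 90%, and surgery on day 85 for everyone. On those assumptions the overstatement is about 1 to 3.5 points at 12 months, always in the favourable direction. Any median that is reached would be too long by about 2.8 months. How far the adjuvant groups are affected unequally depends on the number of early operations, which the documents do not give. The correction is needed before database lock, because otherwise a named secondary endpoint could be reported against its own definition.

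**What to change.** Replace the formula sentence in SAP section 4.4.2 with:

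> For EFS and OS, time (days) = date of event or censoring − date of first study treatment + 1. For DFS, time (days) = date of event or censoring − date of surgery + 1.

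The DFS censoring rules can stay as they are. A patient censored on the date of surgery then has a DFS time of 1 day, as a patient censored on the date of first treatment has for EFS. The change costs one SAP sentence and the matching line in the programming specification. It needs no new data and no change to the sample size. Compared with the formula as written, reported DFS will be slightly less favourable.
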